### **2.5.3 Visit allocation**

The following process will be applied for visit re-allocation. Re-allocated visits will be used in all statistical analyses (descriptive statistics, plots, and statistical models).

No re-allocation will be performed for nominal visits already provided in the clinical database (Visit 1 to Visit 8), and for unscheduled assessments. No reallocation of visit will be performed for PK.

### ***Insulin doses***

In the clinical database, insulin doses transferred from the e-diary will not be assigned to a protocol visit. For the analysis, they will be assigned to the next on-site visit actually performed by the patient after the date of data collection (Visit 3 to Visit 7, or Visit 8000).

### ***End of treatment visit***

If a patient discontinues the treatment prematurely, end of treatment (Visit 8000) assessments will be re-allocated to the next scheduled on-site visit for the patient, except for the PK assessments, as the PK profiles of patients who prematurely discontinued the treatment will not be included in the primary PK analysis.

The next scheduled on-site visit for each patient will be determined as the next on-site visit that should be performed as per protocol, following the last visit actually performed by the patient before Visit 8000.

For a given parameter, the value will not be re-allocated in the following cases:

- If the parameter is not planned to be collected at the re-allocation visit.
- If a value is already available for the parameter at the re-allocation visit.

This process will be used to retrieve all assessments (except PK assessment) performed at the end of treatment visit (Visit 8000) and will apply to insulin doses assigned to Visit 8000 following the process described above.

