- During the period of the COVID-19 (Coronavirus disease 2019) pandemic, protocol deviations may occur due to lockdown restrictions. On-site visits may not be performed according to the protocol schedule for some patients. In such cases, changes in study visit schedule are allowed as needed, to accommodate patient's safe access to study sites and study medication while minimizing risks to trial integrity and data collection: Intermediary on-site visits (Visits 5 and 6) may be replaced by over-the-phone or at-home visits, if feasible.
- The end of treatment visit (Visit 7), which is the most critical one for primary endpoint assessment, may be delayed so that the visit can be conducted on-site while preserving the patient's safety.

Consequently, the open-label treatment period and study duration may be extended by up to approximately 8 weeks, and the assessments collected at "Week 16" visit may be performed up to approximately 24 weeks after randomization. All delayed assessments will be included in the analyses. No risk is foreseen by continuing treatment with IMP beyond the planned 16 weeks in both treatment arms. These changes are temporary and will not be sustained once the pandemic is over. Any delayed assessments will be recorded in the protocol deviations.

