All critical or major protocol deviations (including randomization and drug-dispensing irregularities, see [Section 2.2.1](#)) will be summarized by treatment group among randomized patients (number and percentages). Critical or major protocol deviations will also be summarized according to COVID-19 impact.

Patients impacted by COVID-19 are defined as patients with major impact of COVID-19 on study conduct, including premature EOT/EOS due to COVID-19 and/or critical or major protocol deviations related to COVID-19. The number and percentage of patients impacted or not by COVID-19 will be presented, along with the type of impact, and a listing of participants impacted by COVID-19 will be provided.

A table of patient disposition by visit according to COVID-19 impact will also be provided, based on the eCRF comment page. Each impacted visit will be described according to the following categories:

- Visit not done,
- Visit partially done on site,
- Visit partially done by phone,
- Complete visit but delayed.

Additionally, the analysis populations for pharmacokinetic, immunogenicity, safety and efficacy will be summarized in a table by patient counts on the randomized population:

- PK population as defined in [Section 2.3.1](#),
- Anti-insulin aspart antibody population as defined in [Section 2.3.3](#),
- Safety population as defined in [Section 2.3.2](#),
- Efficacy population: ITT population as defined in [Section 2.3.4](#).

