## **2.4 STATISTICAL METHODS**

Continuous data will be summarized by treatment group (switching arm or non-switching arm) using, if not stated otherwise, the number of observations available (N), mean, SD, minimum, median, and maximum. These apply to all data, except PK data which will be described as detailed in [Section 2.5.7](#).

Categorical and ordinal data (except PK data, see [Section 2.5.7](#)) will be summarized by treatment group (switching arm or non-switching arm) using the number and percentage of patients.

In general, descriptive statistics of parameters (result and change from baseline, if applicable) by scheduled post-baseline visits will be provided on observed cases, ie, including only patients having non-missing assessments at a specific visit. All statistical analyses (descriptive statistics, plots, and statistical models) will be performed on visits defined using the reallocation algorithm of premature end of treatment provided in [Section 2.5.3](#).

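### The SAP assigns early-discontinuation (Visit 8000) data to a week by the last visit performed, not by date, so after a missed visit the exploratory by-visit HbA1c, FPG, antibody and insulin-dose data can carry an earlier week label, and HbA1c, FPG and antibody values can drop out of those summaries

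*SAP*

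**What the plan says.** SAP 2.5.3 (End of treatment visit) sends Visit 8000 assessments, except PK, to the next on-site visit due under the protocol "following the last visit actually performed by the patient before Visit 8000". No study day, date or window enters the rule. A value is not moved in two situations: "If the parameter is not planned to be collected at the re-allocation visit", or "If a value is already available for the parameter at the re-allocation visit". Insulin doses assigned to Visit 8000 follow the same process.

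The rule reaches widely. SAP 2.4 states that all analyses will be "performed on visits defined using the reallocation algorithm of premature end of treatment", and 2.5.3 repeats this for descriptive statistics, plots and models. SAP 2.5.4 keeps unscheduled values out of by-visit summaries.

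The SAP also expects visits to be missed. Its COVID-19 disposition table in 2.2 has the category "Visit not done", and SAP 1.4 says that Visits 5 and 6 "may be replaced by over-the-phone or at-home visits, if feasible". It does not say whether a telephone or at-home contact counts as a visit performed for the re-allocation rule.

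**The concern.** The rule works when every visit before Visit 8000 took place, because the next visit in sequence is then also the next visit by date. Once a visit has been missed the two come apart, and the rule points to a week that has already gone by.

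Two things follow. First, a value can be reported under an earlier week. In the switching arm the weeks carry product meaning: Week 4 closes a NovoLog period, Week 8 the first SAR341402 period, Week 12 a NovoLog period and Week 16 the second SAR341402 period. A sample taken between Weeks 12 and 16 but labelled Week 12 would be read as belonging to the other product. Second, the target visit may be one where the parameter is not scheduled. The value is then not re-allocated and appears in no by-visit summary.

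At stake are the by-visit tables of HbA1c, FPG, AIA status and titer, neutralizing antibodies and insulin dose, and in some patients the Week 16 change from baseline.

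**Working it through.** No stated figure needs reproducing. The check applies the rule to the schedule and enumerates the outcomes.

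**Inputs.** Target days are 28, 56, 84 and 112 for Visits 4 to 7 (protocol 1.3). HbA1c on treatment is scheduled at Visits 3, 5 and 7. FPG and AIA are scheduled at Visits 3, 5, 6 and 7. Insulin dose is reviewed at every on-treatment visit. The re-allocation rule and its two exceptions are in SAP 2.5.3.

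**Method.** Take each last visit performed (3 to 6) and each four-week interval in which Visit 8000 could fall, up to Week 16. SAP target = last visit performed + 1. Comparison rule = the next scheduled visit after the actual date, using nominal weeks.

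**No visit missed (four patterns).** The two rules give the same target in all four.

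**At least one visit missed (six patterns):**

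| Last visit | Missed | Visit 8000 in weeks | SAP target | HbA1c | FPG, AIA | Dose | Date rule |
|---|---|---|---|---|---|---|---|
| 3 | 4 | 4-8 | Visit 4 | not re-allocated | not re-allocated | Week 4 | all Week 8 |
| 3 | 4, 5 | 8-12 | Visit 4 | not re-allocated | not re-allocated | Week 4 | Week 12; HbA1c not re-allocated |
| 3 | 4, 5, 6 | 12-16 | Visit 4 | not re-allocated | not re-allocated | Week 4 | all Week 16 |
| 4 | 5 | 8-12 | Visit 5 | Week 8 | Week 8 | Week 8 | Week 12; HbA1c not re-allocated |
| 4 | 5, 6 | 12-16 | Visit 5 | Week 8 | Week 8 | Week 8 | all Week 16 |
| 5 | 6 | 12-16 | Visit 6 | not re-allocated | Week 12 | Week 12 | all Week 16 |

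**Counts under the SAP rule.** HbA1c: 4 of 6 not re-allocated, 2 of 6 labelled early. FPG and AIA: 3 of 6 not re-allocated (all with Visit 4 missed), 3 of 6 labelled early. Dose: 6 of 6 labelled early, none dropped. Under the date rule HbA1c is unallocated in 2 of 6, and FPG and AIA in none.

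**Size of the displacement.**
- Visit 4 last performed, stop on Day 83: 83 - 56 = 27 days.
- Visit 4 last performed, stop on Day 111: 111 - 56 = 55 days.
- Dose only, Visit 3 last performed, stop on Day 111: 111 - 28 = 83 days.

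SAP 1.4 allows treatment to run to about Week 24, so longer gaps are possible in principle.

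**Number affected.** The documents give no rates. As an assumption, suppose 10% of 184 stop early and 10% to 30% of those had missed the preceding visit: 184 × 0.10 = 18.4, then 18.4 × 0.10 = 1.8 and 18.4 × 0.30 = 5.5, or about 2 to 6 participants.

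**The case against.** Several stronger readings are tempting and do not hold.

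- **Week 16 is lost.** A reader might infer that the Week 16 value goes missing whenever a visit was missed. Participants who stop treatment are asked to stay for the remaining visits (protocol 7.1.1, SAP 1.4), and the efficacy period runs to Visit 7 regardless of discontinuation (SAP 2.1.6). A Visit 7 value serves Week 16 directly. The loss needs a missed visit, an early stop and no Visit 7, so it affects fewer than the 2 to 6 above.
- **The secondary antibody endpoint is distorted.** Treatment-emergent AIA status and peak titer use any on-treatment sample (SAP 2.1.4), so the week label does not change them.
- **Data are discarded.** Values that are not re-allocated are absent from by-visit summaries and possibly from the Week 16 change. The SAP does not say that they are deleted. Insulin doses are only relabelled.
- **COVID-19 replacement visits make it worse.** If a telephone or at-home contact counts as performed, the anchor moves forward and the problem shrinks. The SAP leaves this open.

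Two further objections have weight. The long displacements need repeated missed dispensing visits with treatment continuing through interim or courier resupply, so they are extremes. A date rule also has a cost: with Visit 5 missed and Visit 8000 in weeks 8-12, HbA1c goes to Visit 6, where it is not planned, whereas the present rule keeps it as Week 8.

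What stands is that a stated rule gives the wrong week label in a situation the SAP itself foresees.

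**Conclusion.** The concern holds in a limited form. After a missed visit, the rule in SAP 2.5.3 always targets a week already past. HbA1c, FPG, AIA and insulin-dose data can then be labelled too early, possibly under the other product's period in the switching arm. That last point assumes the product sequence continued on schedule despite the missed dispensing visit. HbA1c can also be left out of by-visit summaries, as can FPG and AIA when Visit 4 was missed.

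Primary PK is exempt from re-allocation. What is affected is tertiary/exploratory, descriptive by-visit reporting with no formal testing, probably in few participants. It does not threaten the trial's main conclusions, but it is worth correcting because the correction is cheap and the week labels carry product meaning.

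**What to change.** Replace the target definition in SAP 2.5.3 with a date rule. Re-allocate Visit 8000, and the insulin doses assigned to it, to the first protocol on-site visit not yet performed whose target day plus window is on or after the study day of Visit 8000. With the protocol windows the upper limits are 28 + 2 = Day 30, 56 + 2 = Day 58, 84 + 2 = Day 86 and 112 + 3 = Day 115. Send any Visit 8000 after Day 115 to Visit 7, since SAP 1.4 permits extended treatment and a bare date rule would leave such data without a target. The words *not yet performed* matter: without them, a participant who attended Visit 5 on Day 56 and stopped on Day 57 would be sent back to Visit 5 and blocked by the value already there.

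Keep the exception for a value already available. If the exception for unplanned parameters is also kept, list the affected values separately, in particular HbA1c taken in weeks 8-12 after a missed Visit 5. State whether telephone or at-home visits count as performed. In passing, correct SAP 2.1.4, 2.1.5 and 2.1.6, which cite Section 2.5.1 for a process described in 2.5.3.

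The cost is a few sentences and a small change to the derivation program before database lock. No new data are needed, and results do not change for participants with no missed visit.

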#### **2.5.4 Unscheduled visits**

The determination of baselines for safety and efficacy parameter variables is based on all measurements from both scheduled and unscheduled visits (measurements from the central laboratory only), as mentioned in [Section 2.5.3](#). The determination of the last on-treatment value for safety parameters is also based on all assessments from both scheduled and unscheduled visits (measurements from the central laboratory only).

Measurements from the unscheduled visits (measurements from the central laboratory only) are also considered for PCSA summary of safety parameters.

Unscheduled visit measurements are not included in the by-visit summaries.

#### **2.5.5 Pooling of centers for statistical analyses**

All centers will be pooled for statistical analysis. Centers will not be taken into account in the statistical analysis.

#### **2.5.6 Study-specific conventions**

In the statistical appendices and in-text tables, the following treatment labels will be used:

- Switching arm
- Non-Switching arm

## **2.5.7 Handling for pharmacokinetic data**

### **2.5.7.1 *Individual PK parameters***

Individual PK parameters will be provided by a vendor.

AUC values extrapolated by more than 20% will be excluded from any pharmacokinetic statistical analysis.

### **2.5.7.2 *Descriptive analyses***

Descriptive analyses and graphical descriptive display of PK parameters will be provided by a vendor, under responsibility of PK function.

For ease of presentation, mean values will be arithmetic mean unless specified.

Individual concentration values below the lower limit of quantification (LLOQ) will be treated as zero in calculating mean values but reported as <LLOQ. Mean values below LLOQ will be reported as <LLOQ in the tables.

Mean calculations and their associated statistics will be generated from unrounded numbers and may differ slightly from those values that would be determined using the rounded numbers displayed in the tables.

Values expressed in tables will be for ease of presentation and will not be meant to imply accuracy to more than 3 significant figures.

Plasma concentrations and pharmacokinetic parameters will be summarized by arithmetic mean, geometric mean, SD, SE, CV(%), minimum, median, maximum, and number of observations by treatment.

## **2.5.8 Statistical technical issues**

Not applicable.

### **3 INTERIM ANALYSIS**

No interim analysis is planned.

## 4 DATABASE LOCK

It is planned to lock the database approximately 7 weeks after the last patient last visit (LPLV).

## 5 SOFTWARE DOCUMENTATION

Descriptive analyses for PK parameters will be generated using version 6.4 of Phoenix WinNonlin.

All other summaries and statistical analyses will be generated using SAS 9.4 or higher.

## 7 LIST OF APPENDICES

[Appendix A:](#) Potentially clinically significant abnormalities criteria

## Appendix A Potentially clinically significant abnormalities criteria

---

**CRITERIA for POTENTIALLY CLINICALLY SIGNIFICANT ABNORMALITIES  
for phase 2/3 studies (oncology excepted)**

---

Parameter	PCSA	Comments
Clinical Chemistry		
ALT	By distribution analysis : >3 ULN >5 ULN >10 ULN >20 ULN	Enzymes activities must be expressed in ULN, not in IU/L. Concept paper on DILI – FDA draft Guidance Oct 2007. Internal DILI WG Oct 2008. Categories are cumulative. First row is mandatory. Rows following one mentioning zero can be deleted.
AST	By distribution analysis : >3 ULN >5 ULN >10 ULN >20 ULN	Enzymes activities must be expressed in ULN, not in IU/L. Concept paper on DILI – FDA draft Guidance Oct 2007. Internal DILI WG Oct 2008. Categories are cumulative. First row is mandatory. Rows following one mentioning zero can be deleted.
Alkaline Phosphatase	>1.5 ULN	Enzymes activities must be expressed in ULN, not in IU/L. Concept paper on DILI – FDA draft Guidance Oct 2007. Internal DILI WG Oct 2008.
Total Bilirubin	>1.5 ULN >2 ULN	Must be expressed in ULN, not in $\mu$ mol/L or mg/L. Categories are cumulative. Concept paper on DILI – FDA draft Guidance Oct 2007. Internal DILI WG Oct 2008.

---

**CRITERIA for POTENTIALLY CLINICALLY SIGNIFICANT ABNORMALITIES  
for phase 2/3 studies (oncology excepted)**

Parameter	PCSA	Comments
Conjugated Bilirubin	>35% Total Bilirubin and TBILI>1.5 ULN	Conjugated bilirubin dosed on a case-by-case basis.
ALT and Total Bilirubin	ALT>3 ULN and TBILI>2 ULN	Concept paper on DILI – FDA draft Guidance Oct 2007. Internal DILI WG Oct 2008. To be counted within a same treatment phase, whatever the interval between measurements.
CPK	>3 ULN >10 ULN	FDA Feb 2005. Am J Cardiol April 2006. Categories are cumulative. First row is mandatory. Rows following one mentioning zero can be deleted.
CLcr (mL/min) (Estimated creatinine clearance based on the Cokcroft-Gault equation)	<15 (end stage renal disease) ≥15 - <30 (severe decrease in GFR) ≥30 - < 60 (moderate decrease in GFR) ≥60 - <90 (mild decrease in GFR) ≥ 90 (normal GFR)	FDA draft Guidance 2010 Pharmacokinetics in patients with impaired renal function- study design, data analysis, and impact on dosing and labeling
eGFR (mL/min/1.73m  ) (Estimate of GFR based on an MDRD equation)	<15 (end stage renal disease) ≥15 - <30 (severe decrease in GFR) ≥30 - < 60 (moderate decrease in GFR) ≥60 - <90 (mild decrease in GFR) ≥ 90 (normal GFR)	FDA draft Guidance 2010 Pharmacokinetics in patients with impaired renal function- study design, data analysis, and impact on dosing and labeling
Creatinine	≥150 µmol/L (Adults) ≥30% change from baseline ≥100% change from baseline	Benichou C., 1994.

**CRITERIA for POTENTIALLY CLINICALLY SIGNIFICANT ABNORMALITIES  
for phase 2/3 studies (oncology excepted)**

Parameter	PCSA	Comments
Uric Acid		Harrison- Principles of internal Medicine 17 th Ed., 2008.
Hyperuricemia	>408 µmol/L	
Hypouricemia	<120 µmol/L	
Blood Urea Nitrogen	≥17 mmol/L	
Chloride	<80 mmol/L >115 mmol/L	
Sodium	≤129 mmol/L ≥160 mmol/L	
Potassium	<3 mmol/L ≥5.5 mmol/L	FDA Feb 2005.
Total Cholesterol	≥7.74 mmol/L	Threshold for therapeutic intervention.
Triglycerides	≥4.6 mmol/L	Threshold for therapeutic intervention.
Lipasemia	≥3 ULN	
Amylasemia	≥3 ULN	
Glucose		
Hypoglycaemia	≤3.9 mmol/L and <LLN	ADA May 2005.
Hyperglycaemia	≥11.1 mmol/L (unfasted); ≥7 mmol/L (fasted)	ADA Jan 2008.
HbA1c	>8%	
Albumin	≤25 g/L	
CRP	>2 ULN or >10 mg/L (if ULN not provided)	FDA Sept 2005.

**CRITERIA for POTENTIALLY CLINICALLY SIGNIFICANT ABNORMALITIES  
for phase 2/3 studies (oncology excepted)**

Parameter	PCSA	Comments
Hematology		
WBC	<3.0 Giga/L (Non-Black); <2.0 Giga/L (Black) ≥16.0 Giga/L	Increase in WBC: not relevant. To be interpreted only if no differential count available.
Lymphocytes	>4.0 Giga/L	
Neutrophils	<1.5 Giga/L (Non-Black); <1.0 Giga/L (Black)	International Consensus meeting on drug-induced blood cytopenias, 1991. FDA criteria.
Monocytes	>0.7 Giga/L	
Basophils	>0.1 Giga/L	
Eosinophils	>0.5 Giga/L or >ULN (if ULN≥0.5 Giga/L)	Harrison- Principles of internal Medicine 17 th Ed., 2008.
Hemoglobin	≤115 g/L (Male); ≤95 g/L (Female) ≥185 g/L (Male); ≥165 g/L (Female)  Decrease from Baseline ≥20 g/L	Criteria based upon decrease from baseline are more relevant than based on absolute value. Other categories for decrease from baseline can be used (≥30 g/L, ≥40 g/L, ≥50 g/L).
Hematocrit	≤0.37 v/v (Male) ; ≤0.32 v/v (Female) ≥0.55 v/v (Male) ; ≥0.5 v/v (Female)	
RBC	≥6 Tera/L	Unless specifically required for particular drug development, the analysis is redundant with that of Hb. Otherwise, consider FDA criteria.
Platelets	<100 Giga/L ≥700 Giga/L	International Consensus meeting on drug-induced blood cytopenias, 1991.

**CRITERIA for POTENTIALLY CLINICALLY SIGNIFICANT ABNORMALITIES  
for phase 2/3 studies (oncology excepted)**

Parameter	PCSA	Comments
Urinalysis		
pH	≤4.6 ≥8	
Vital signs		
HR	≤50 bpm and decrease from baseline ≥20 bpm ≥120 bpm and increase from baseline ≥20 bpm	To be applied for all positions (including missing) except STANDING.
SBP	≤95 mmHg and decrease from baseline ≥20mmHg ≥160 mmHg and increase from baseline ≥20 mmHg	To be applied for all positions (including missing) except STANDING.
DBP	≤45 mmHg and decrease from baseline ≥10 mmHg ≥110 mmHg and increase from baseline ≥10 mmHg	To be applied for all positions (including missing) except STANDING.
Orthostatic Hypotension		
Orthostatic SDB		
Orthostatic DBP	≤-20 mmHg ≤-10 mmHg	
Weight	≥5% increase from baseline ≥5% decrease from baseline	FDA Feb 2007.

**CRITERIA for POTENTIALLY CLINICALLY SIGNIFICANT ABNORMALITIES  
for phase 2/3 studies (oncology excepted)**

Parameter	PCSA	Comments
ECG		Ref.: ICH E14 guidance (2005) and E14 Q&A (2012), and Cardiac Safety Research Consortium White Paper on PR and QRS (Nada et al. Am Heart J. 2013; 165(4) : 489-500)
HR	
<50 bpm
 
<50 bpm and decrease from baseline ≥20 bpm
 
<40 bpm
 
<40 bpm and decrease from baseline ≥20 bpm
 
<30 bpm
 
<30 bpm and decrease from baseline ≥20 bpm
 
>90 bpm
 
>90 bpm and increase from baseline ≥20bpm
 
>100 bpm
 
>100 bpm and increase from baseline ≥20bpm
 
>120 bpm
 
>120 bpm and increase from baseline ≥20 bpm
	Categories are cumulative
PR	
>200 ms
 
>200 ms and increase from baseline ≥25%
 
> 220 ms
 
>220 ms and increase from baseline ≥25%
 
> 240 ms
 
> 240 ms and increase from baseline ≥25%
	Categories are cumulative

**CRITERIA for POTENTIALLY CLINICALLY SIGNIFICANT ABNORMALITIES  
for phase 2/3 studies (oncology excepted)**

Parameter	PCSA	Comments
QRS	>110 ms >110 msec and increase from baseline $\geq 25\%$ >120 ms >120 ms and increase from baseline $\geq 25\%$	Categories are cumulative
QT	>500 ms	
QTc	Absolute values (ms)  >450 ms >480 ms >500 ms  Increase from baseline Increase from baseline $]30-60]$ ms Increase from baseline $>60$ ms	To be applied to any kind of QT correction formula. Absolute values categories are cumulative  QTc $>480$ ms and $\Delta QTc >60$ ms are the 2 PCSA categories to be identified in individual subjects/patients listings.

Signature Page for VV-CLIN-0540289 v3.0  
efc15178-16-1-9-sap

Approve & eSign

Clinical
